#### 5.4 Translational Medicine Criteria

- a. Patients must be offered the opportunity to participate in specimen banking for future use to include the translational medicine studies outlined in [Section 15.0](#).

#### 5.5 Regulatory Criteria

- a. All patients must be informed of the investigational nature of this study and must sign and give written informed consent in accordance with institutional and federal guidelines.
- b. As part of the OPEN registration process (see [Section 13.4](#) for OPEN access instructions) the treating institution's identity is provided in order to ensure that the current (within 365 days) date of institutional review board approval for this study has been entered into the data base.

## 6.0 STRATIFICATION FACTORS

Patients will be randomized using a dynamic balancing algorithm (45) with stratification based on:

- a. Risk group based on pathologic stage (intermediate high-risk vs very high risk) (see [Section 4.0](#)),
- b. Histology (clear cell vs non-clear cell); (NOTE: The tumor will be classified as clear cell if **any** component of clear cell histology is identified in the specimen.)
- c. Performance status (0 vs 1).

## 7.0 TREATMENT PLAN

For treatment or dose modification related questions, please contact [name] at [name] or [name] at [name]. For dosing principles or questions, please consult the SWOG Policy #38 "Dosing Principles for Patients on Clinical Trials" at <http://swog.org> (then click on "Policies and Manuals" under the "Visitors" menu and choose Policy #38).

### 7.1 Good Medical Practice

The following tests (and/or assessments) are recommended within 28 days prior to registration in accordance with Good Medical Practice. Results of these tests do not determine eligibility and minor deviations from normal limits would be acceptable if they do not affect patient safety in the clinical judgment of the treating physician. If there are significant deviations in these tests/assessments that could impact on patient safety, it is highly recommended that the registering investigator discuss the patient with the Study Chair prior to registering.

- a. Patients should not have an uncontrolled intercurrent illness including, but not limited to active bleeding diathesis, uncontrolled infection/disorders, nonmalignant medical illnesses that are uncontrolled or whose control may be jeopardized by the treatment with the study therapy, or psychiatric illness/social situations that would limit compliance with study requirements.
- b. Testing for hepatitis B viral load and serologic markers: HBV-DNA, HBsAg, HBs Ab, and HBc Ab should be performed at screening for all patients with the following risk factors (see [Section 7.3](#) and [8.6](#)):
  - Patients who currently live in (or have lived in) Asia, Africa, Central and South America, Eastern Europe, Spain, Portugal, and Greece.
  - known or suspected past hepatitis B infection,
  - blood transfusion(s) prior to 1990,
  - current or prior IV drug users,
  - current or prior dialysis,
  - current or prior high-risk sexual activity,
  - body piercing (other than ear piercing) or tattoos,
  - mother known to have hepatitis B
  - history suggestive of hepatitis B infection, e.g., dark urine, jaundice, right upper quadrant pain.
  - Additional patients at the discretion of the investigator
  - household contact with hepatitis B infected patient(s),

Testing for hepatitis C should be performed using quantitative RNA-PCR at screening for patients with the following risk factors (see [Section 8.6](#)):

- known or suspected past hepatitis C infection (including patients with past interferon 'curative' treatment),
  - blood transfusions prior to 1990,
  - current or prior IV drug users,
  - current or prior dialysis,
  - household contact of hepatitis C infected patient(s),
  - current or prior high-risk sexual activity,
  - body piercing other than ear piercing or tattoos,
  - Additional patients at the discretion of the investigators
- c. Coadministration of moderate CYP3A4 inhibitors (such as erythromycin, fluconazole, calcium channel blockers, benzodiazepines) and inducers (such as bamazepine, phenobarbital) should be avoided if possible, or used subject to caution. Coadministration with substrates, inducers, or inhibitors of P-glycoprotein should be avoided if possible, or used subject to caution. See [Appendix 18.3](#). Grapefruit and grapefruit juice affect cytochrome P450 and P-glycoprotein activity and should be avoided.
- d. Alkaline phosphatase obtained.

## 7.2 Treatment Schedule

All patients will be randomized to receive either everolimus or placebo daily for nine, six week cycles.

AGENT	DOSE	ROUTE	DAYS	DURATION
Everolimus or Matched Placebo	10 mg (two 5 mg Tablets)	Oral	Every Day	378 days (54 weeks)

\* Everolimus (or matched placebo) tablets are supplied as 5 mg tablets.

Everolimus must be administered orally, once daily preferably in the morning with a glass of water and no more than a light fat-free meal. Tablets must be swallowed whole with a glass of water. The tablets must not be chewed or crushed, and grapefruit or citrus juices should be avoided.

A cycle of treatment is six weeks. Assessment for the primary endpoint (recurrence) must occur after every three cycles (18 weeks) for 54 weeks, then every six months for two years, and then annually thereafter until recurrence, death, or 10 years after registration, whichever comes first (regardless whether patient is still on active protocol treatment). Recurrence assessments consist of physical exams and CT scans.

Radiographic assessment for pneumonitis must be undertaken as per [Section 8.4c](#).

## 7.3 Concomitant Therapy

All medications taken other than study drugs and significant non-drug therapies (including physical therapy and blood transfusions) must be recorded. If concomitant therapy must be added or changed, the reason and name of the drug/therapy must be documented in the "comments" section of the **S0931** Treatment Form.

In general, the use of any concomitant medication/therapies deemed necessary for the care of the patient are allowed, including drugs given prophylactically (e.g. antiemetics ± steroids), with the following exceptions:

- No other investigational therapy must be given to patients.
- No chronic treatment with systemic steroids or another immunosuppressive agent. Topical or inhaled corticosteroids are allowed.
- No anticancer agents other than the study medications administered as part of this study protocol must be given to patients. If such agents are required for a patient then the patient must be withdrawn from protocol treatment.
- Growth factors (e.g. G-CSF, G-GM-CSF, erythropoietin, platelets growth factors etc.) are not to be administered prophylactically but may be prescribed by the treating physician for rescue from severe hematologic events.
- Live vaccines must not be administered to patient due to immunosuppressant potential of everolimus.
- Drugs known to be strong inhibitors or inducers of the isoenzyme CYP3A4 must not be administered as systemic therapy (see [Section 5.2e](#)). Drugs or substances known to be moderate inhibitors or inducers of CYP3A (see [Appendix 18.3](#)) should be avoided if possible or used subject to caution as these can alter everolimus metabolism. Co-administration with strong or moderate inhibitors of P-glycoprotein (PgP) (see [Appendix 18.3](#)) should be avoided if possible, or used subject to caution. Seville orange, star fruit, grapefruit and their juices affect P450 and PgP activity. Concomitant use should be avoided.
- It is highly recommended that patients positive HBV-DNA or HBsAg are treated prophylactically with an antiviral for 1-2 weeks prior to receiving study drug (see [Section 8.5](#)).
- The antiviral treatment should continue throughout the entire study period and for at least 4 weeks after the last dose of study drug.
- Patients on antiviral prophylaxis treatment or positive HBV antibodies should be tested for HBV-DNA according to study visit schedule (See [Section 8.6](#) and [9.0](#)).

#### 7.4 Intake Calendar

Everolimus drug compliance will be recorded on a treatment Intake Calendar (see [Appendix 18.4](#)). Institutional CRAs will review and ascertain patient adherence with protocol therapy at the end of treatment for each cycle. Calendar should be kept in the patient's clinic chart. Sites utilizing the CIRB must use the Intake Calendar provided. Sites not utilizing the CIRB may use institutional pill diaries or other source documentation in place of Intake Calendar at the discretion of the treating physician.

#### 7.5 Unblinding Procedures

The procedures for emergency unblinding are outlined in [Appendix 18.2](#). Patients who have recurrence of disease as defined in [Section 10.1](#) have the option to be unblinded in planned fashion, as described in this section. Emergency unblinding will be done for anything other than recurrence as defined in [Section 10.1](#). Patients who undergo optional treatment unblinding and are found to have been randomized to “placebo” will not receive investigational-supplied everolimus. Novartis Pharmaceutical Corporation will NOT provide investigational supplies of everolimus once a patient has been unblinded.

##### a. Criteria for Planned Unblinding:

The planned unblinding procedure applies to patients who experience recurrence as defined in [Section 10.1](#). It is vital to properly apply the protocol specified definition of recurrence. If any questions arise with regard to recurrence for a patient, please contact the GU Data Coordinator in Seattle by e-mail at [[contact]](mailto:[contact]) or by telephone at [name], 6:30 a.m. to 4:00 p.m. Pacific Time, Monday through Friday, excluding holidays.

Prior to requesting a planned unblinding, the following forms must be submitted and processed by the SWOG Data Operations Office:

Off Treatment Notice

**S0931** Recurrence Assessment Form

Radiology report(s) supporting recurrence (see [Section 10.1](#))

Pathology report(s) supporting recurrence (see [Section 10.1](#))

Please submit all required forms to the SWOG Data Operations Center ([[contact]](mailto:[contact])) with the subject line "**S0931** Patient #XXXXXX, Requesting Planned Unblinding". Please allow a minimum of 2 working days for review of forms.

[name] (or [name]) will provide a written confirmation to the site that the patient has an adequately documented recurrence. This documentation should be placed in the patient's chart.

b. Planned Unblinding Procedures

You may unblind patients at time of disease recurrence from Member, Affiliate, and CCOP institutions to a Therapeutics study using the SWOG planned unblinding program. To access the planned unblinding program go to the SWOG Web site (<http://swog.org>) and click on the *Logon* link to go to the SWOG Members Area logon page (<https://swog.org/members/logon.asp>). This Web program is available at any time except for periods listed under *Down Times*. Log on as an Individual User using your SWOG Roster ID Number and individual web user password. Help for the logon process may be found at <https://swog.org/members/logonhelp.asp>. After you have logged on, click on the *Workbenches* link, then the *CRA Workbench* link, and then the *Planned Unblinding* link. Go to the Entry Page for the Planned Unblinding program. The CRA must have the SWOG ID number, initials, and investigator number available for the unblinding.

To unblind a patient at disease recurrence, you must meet the following criteria (in order):

1. You are entered into the SWOG Roster and issued a SWOG Roster ID Number.
2. You are associated as an investigator or CRA/RN to the institution where a planned unblinding is occurring.
3. You are granted permission to use the Planned Unblinding program at that institution.

For assistance with points 1 and 2 call the SWOG Operations Office at [name]. For point 3 you must contact your Web User Administrator. Each SWOG institution has one or more Web User Administrators who may set up Web Users at their institution and assign permissions and passwords to these users.

Non-SWOG sites may unblind patients at time of disease recurrence using the following url: <https://crawb.crab.org/TXWB/ctsulogon.aspx>.

If the Web Planned Unblinding program is not used, the planned unblinding must be done by phone.

Member, Affiliate and CCOP Institutions

Planned unblinding by phone of patients from Member, Affiliate and CCOP institutions must be done through the SWOG Data Operations Center in Seattle by telephoning

[name], 6:30 a.m. to 4:00 p.m. Pacific Time, Monday through Friday, excluding holidays.

NOTE: When unblinding **S0931** patients in the SWOG Planned Unblinding Program leave "Bottle ID" field blank.

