#### 7.6 Criteria for Removal from Protocol Treatment

- a. Recurrence of disease or symptomatic deterioration (as defined in [Section 10.0](#)). If the patient has documented recurrence as defined in [Section 10.1](#), unblinding of study treatment as outlined in [Section 7.5](#) may be requested.
- b. Unacceptable toxicity defined as any toxicity requiring discontinuation of study drug per [Section 8.0](#). If a patient is removed from protocol treatment due to toxicity, he/she must continue to be followed for recurrence according to the same schedule as detailed in [Sections 7.2](#) and [9.0](#) (every 4 months [18 weeks] during Year 1 (regardless whether patient is still on active protocol treatment), then every six months for Years 2 and 3, and then annually thereafter until recurrence, death, or 10 years after registration, whichever comes first. Recurrence assessments consist of physical exams and CT scans)
- c. Delay in protocol treatment > 21 days due to pneumonitis or > 28 days due to any other reason. If a patient is removed from protocol treatment due to toxicity, the must continue to be followed for recurrence according to the same schedule as detailed in [Sections 7.2](#) and [9.0](#) (every 4 months [18 weeks] during Year 1 (regardless whether patient is still on active protocol treatment), then every six months for two years, and then annually thereafter until recurrence, death, or 10 years after registration, whichever comes first. Recurrence assessments consist of physical exams and CT scans)
- d. Completion of nine cycles of protocol treatment.
- e. The patient may withdraw from the study at any time for any reason.

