#### 14.4 Data Submission Overview and Timepoints

- a. WITHIN 7 DAYS OF REGISTRATION:

Submit copies of the following:

**S0931** Prestudy Form

**S0931** Tumor Specimen Processing Form (for patients who consent to the translational medicine studies)

Surgical and Radiology Reports

Pathology Report confirming renal cell carcinoma including subtypes.

- b. IF PATIENT CONSENTED:

Submit specimens within 28 days of obtaining as outlined in [Section 15.0](#).

- c. WITHIN 7 DAYS OF COMPLETION OF EACH CYCLE (EVERY SIX WEEKS) WHILE ON PROTOCOL TREATMENT:

**S0931** Treatment Form

**S0931** Adverse Event Form

- d. EVERY EIGHTEEN WEEKS FOR THE FIRST 54 WEEKS (REGARDLESS OF EARLY PROTOCOL TREATMENT DISCONTINUATION), AND THEN EVERY 6 MONTHS FOR THE FOLLOWING 2 YEARS, AND THEN ANNUALLY UNTIL 10 YEARS AFTER REGISTRATION, RECURRENCE OR DEATH WHICHEVER COMES FIRST:

**S0931** Recurrence Assessment Form

- e. WITHIN 14 DAYS OF DISCONTINUATION OF ALL PROTOCOL TREATMENT:

Off Treatment Notice

Final **S0931** Treatment Form

Final **S0931** Adverse Event Form

- f. AFTER OFF ALL PROTOCOL TREATMENT, EVERY SIX MONTHS FOR TWO YEARS AND ANNUALLY UNTIL TEN YEARS AFTER REGISTRATION OR UNTIL DEATH:

Submit copies of the **S0931** Specific Follow Up Form

- g. WITHIN 14 DAYS OF RECURRENCE:
- S0931** Adverse Event Form
- Off Treatment Notice
- If patient was off protocol treatment:
- S0931** Specific Follow-Up Form
- For all patients:
- S0931** Recurrence Assessment Form
- Radiology and pathology reports documenting recurrence.
- h. WITHIN 4 WEEKS OF KNOWLEDGE OF DEATH:
- If patient was still on protocol treatment:
- Notice of Death
- Final S0931** Treatment Form
- Final S0931** Adverse Event Form
- If patient was off protocol treatment:
- Notice of Death
- S0931** Specific Follow-Up Form

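### Planned unblinding at recurrence does not wait for the final Adverse Event and Treatment Forms, so the last cycle's toxicity can be graded by site staff who know the arm

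*Combined protocol and SAP*

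**What the plan says.** Section 7.6a makes recurrence a reason to stop protocol treatment and allows a request for unblinding at that point. Section 7.5a sets the conditions: "Prior to requesting a planned unblinding, the following forms must be submitted and processed by the SWOG Data Operations Office". Four items follow: the Off Treatment Notice, the S0931 Recurrence Assessment Form, and the radiology and pathology reports that support recurrence. On timing it adds: "Please allow a minimum of 2 working days for review of forms". The sponsor's staff then "will provide a written confirmation to the site that the patient has an adequately documented recurrence". That confirmation concerns recurrence only.

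The assignment goes to the treating site. Among the conditions for using the unblinding program, Section 7.5b has: "You are associated as an investigator or CRA/RN to the institution where a planned unblinding is occurring".

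Section 14.4 sets the form deadlines:

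- 14.4c: Treatment and Adverse Event Forms, "WITHIN 7 DAYS OF COMPLETION OF EACH CYCLE (EVERY SIX WEEKS) WHILE ON PROTOCOL TREATMENT".
- 14.4e: Off Treatment Notice, final Treatment Form and final Adverse Event Form, "WITHIN 14 DAYS OF DISCONTINUATION OF ALL PROTOCOL TREATMENT".
- 14.4g: Adverse Event Form, Off Treatment Notice, Recurrence Assessment Form and supporting reports (no Treatment Form), "WITHIN 14 DAYS OF RECURRENCE".

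None of these deadlines is tied to the date of unblinding. Sections 7.6, 8.9, 16.1 and 18.2 contain no rule that toxicity forms must be in before a planned unblinding.

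**The concern.** The trial is double-blind, and Section 1.2b makes the toxicity comparison between arms a secondary objective. Section 7.5a protects the primary endpoint by having recurrence documented and confirmed before the arm is disclosed. It gives toxicity no matching protection. Section 14.4e lists the Off Treatment Notice beside the two final forms, but only the notice was carried into the 7.5a list, which looks like an oversight.

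A site that follows both sections to the letter can obtain the assignment and then complete the last interval's CTCAE grades and treatment record. Several of the frequent everolimus toxicities in the Section 11.5 table need judgement to grade, for example oral mucositis (35% at Grade 2-4) and fatigue (19%). Knowledge of the arm could push grades up on everolimus and down on placebo. The last interval can also set a patient's worst grade.

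**Working it through.** The plan states no figure for this point, so there is none to reproduce. The check has two parts.

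**Order of events.**

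| Item | Required before planned unblinding (7.5a) | Deadline (14.4) |
|---|---|---|
| Off Treatment Notice | yes | 14 days (e, g) |
| Recurrence Assessment Form | yes | 14 days (g) |
| Radiology and pathology reports | yes | 14 days (g) |
| Final Adverse Event Form | no | 14 days (e; g asks for an Adverse Event Form) |
| Final Treatment Form | no | 14 days (e) |
| Forms for a completed cycle | no | 7 days (c) |

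Two working days are 2 to 4 calendar days. If the four items go in as soon as treatment stops, the arm can be known while the final forms are still open for up to 14 − 4 = 10 to 14 − 2 = 12 days. If the last interval is a completed cycle under the 7-day rule, 7 − 4 = 3 to 7 − 2 = 5 days remain.

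**Ceiling on patients.** Inputs:

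- 732 eligible patients per arm, placebo median RFS 4.9 years and hazard ratio 0.82 (Section 11.1, July 2015 revision).
- Control hazard 0.1027 per year (Section 11.2, December 2020 update).
- 54 weeks of treatment (Section 7.2), T = 54 × 7 / 365.25 = 1.035 years.
- Everolimus losses to refusal or toxicity of 25%, 41% and 52% by 3, 6 and 12 months (Section 11.5), so 75%, 59% and 48% remain on drug.

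Placebo, no dropout, probability of an RFS event = 1 − exp(−hazard × T):

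- Hazard ln 2 / 4.9 = 0.1415: 1 − exp(−0.1464) = 13.6%, or 100 of 732.
- Hazard 0.1027: 1 − exp(−0.1063) = 10.1%, or 74 of 732.

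Everolimus, hazard × 0.82. With no dropout the figures would be 11.3% (83) and 8.4% (61). The event density is then weighted by the fraction still on drug, linear between the stated points and flat after 12 months:

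- Hazard 0.1160: 7.4%, or 54 of 732.
- Hazard 0.0842: 5.4%, or 40 of 732.

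Hand check: time on drug is 0.875 × 0.25 + 0.67 × 0.25 + 0.535 × 0.5 + 0.48 × 0.035 = 0.67 years per patient. Then 0.67 × 0.1160 = 7.8% and 0.67 × 0.0842 = 5.6%. Both are slightly above the integrated values, as expected, because the hand check ignores patients who have already had an event.

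Patients who recur in the 14 days after stopping drug, before the final forms are due, are outside this count. They add at most 732 × [1 − exp(−0.1415 × 14/365.25)] = about 4 per arm.

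**The case against.** The case for leaving this alone has several sound parts.

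- **Earlier cycles are covered.** Under 14.4c each completed cycle is reported within 7 days, and scheduled scans fall every three cycles, at cycle boundaries. The full 14-day window mainly concerns recurrences found between scans. This stands, and it limits the exposure to the last, usually partial, cycle.
- **Fast unblinding is not typical.** Section 10.1 asks for biopsy where possible and, for several sites without biopsy, repeat scans showing growth. Section 14.4g puts the Adverse Event Form in the same packet as the four 7.5a items, so many sites will send everything together. This stands as a statement about likely practice, but no rule requires that order.
- **Part of the record is hard to alter.** Cholesterol, triglycerides and glucose are laboratory values, and patients note tablets and side effects on the Intake Calendar. This stands for those items. It does not cover the site's grading of mucositis, fatigue or rash.
- **Changing 7.5a now is late.** The December 2020 update describes 4.5 years of accrual, six more years of follow-up and a final analysis expected by March 2022. Six years back from 2021-2022 puts the last registration at about 2015-2016, and treatment lasted 54 weeks. Almost certainly nobody can still recur on study drug. This stands, and it shifts the weight to the retrospective check.

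A reader might also infer that attribution of events is biased. The Adverse Event Form's content is not in the documents, and attribution appears explicitly only for expedited reporting (Section 16.1, Table 16.1). The point rests on grading and the treatment record alone.

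**Conclusion.** The gap is real but narrow. For patients who recur on protocol treatment, or before their final forms are in, the last interval's CTCAE grading and treatment record can be completed by site staff who know the arm. Only the secondary toxicity comparison is exposed.

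Two stronger readings should be resisted. One is that recurrence-free survival is compromised: the documents do not support this, because recurrence must be documented and confirmed in writing before disclosure. The other is that 114 to 154 patients (74 + 40 to 100 + 54) had toxicity graded unblinded. That sum is only a loose ceiling. It uses the RFS hazard, and RFS counts death from any cause (Section 10.4), whereas a patient who dies without recurrence is never a candidate for planned unblinding. It sets placebo dropout to zero and counts only refusal and toxicity losses on everolimus. Unblinding is optional, and many sites will file all forms together. It also assumes exponential RFS and treatment starting at registration.

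The documents give no share of sites that would unblind first, so neither the number actually affected nor the effect on any toxicity rate can be estimated. The direction of bias described above is a plausible expectation, not something the documents show.

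**What to change.** In Section 7.5a, add the final S0931 Adverse Event Form and the final S0931 Treatment Form to the required list, for patients who recur on protocol treatment or before those forms are in. Both are already mandatory, so only their order changes. The cost is one line of text and a short wait for planned unblinding when a site's forms are late. Emergency unblinding under Section 18.2 is unaffected.

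For patients already unblinded, flag adverse-event records first entered or changed after the unblinding date, and repeat the toxicity table without them as a sensitivity analysis. Report the number flagged by arm. This assumes that entry and unblinding dates are held. Section 18.2c has every unblinding recorded on the Off Treatment Notice, but 7.5a has that notice submitted before the request, so the date may have to come from the planned unblinding program. The cost is one data query and one extra table.
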